#### **For the liver events:**

- Repeating the LFT to confirm elevation as appropriate
- Discontinuation of the investigational drug (refer to [Section 7.1](#), if appropriate)
- Hospitalization of the subject if appropriate
- A causality assessment of the liver event via exclusion of alternative causes (e.g. disease, co-medications)
- An investigation of the liver event which needs to be followed until resolution.

These investigations can include serology tests, imaging and pathology assessments, hepatologist's consultancy, based on investigator's discretion. All follow-up information, and the procedures performed should be recorded as appropriate in the CRF, including the liver event overview CRF pages.

## **9.4      Pregnancy reporting**

To ensure patient safety, each pregnancy in a subject on study drug must be reported to Novartis within 24 hours of learning of its occurrence. The pregnancy should be followed up to determine outcome, including spontaneous or voluntary termination, details of the birth, and the presence or absence of any birth defects, congenital abnormalities, or maternal and/or newborn complications. The study drug must be discontinued, though the subject may stay in the study, if she wishes to do so. All assessments that are considered as a risk during pregnancy must not be performed. The subject may continue all other protocol assessments. Pregnancy must be recorded on a Pharmacovigilance Pregnancy Form and reported by the investigator to the local Novartis Drug Safety and Epidemiology Department. Pregnancy follow-up should be recorded on the same form and should include an assessment of the possible relationship to the Novartis study drug of any pregnancy outcome. Any SAE experienced during pregnancy must be reported on an SAE Report Form.

## **9.5      Early phase safety monitoring**

The Investigator will monitor adverse events in an ongoing manner and inform the Sponsor of any clinically relevant observations. Any required safety reviews will be made jointly between medically qualified personnel representing the Sponsor and Investigator. Such evaluations may occur verbally, but the outcome and key discussion points will be summarized in writing (e-mail) and made available to both Sponsor and all Investigator(s). Criteria pertaining to stopping the study/treatment or adapting the study design are presented above.

When two or more clinical site(s) are participating in the clinical study, the Sponsor will advise the Investigator(s) at all sites in writing (e-mail) (and by telephone if possible) of any new, clinically relevant safety information reported from another site during the conduct of the study in a timely manner.

# **10      Data review and database management**

## **10.1    Site monitoring**

Before study initiation, at a site initiation visit or at an investigator's meeting, a Novartis representative will review the protocol and CRFs with the investigators and their staff. During the study Novartis employs several methods of ensuring protocol and GCP compliance and the quality/integrity of the sites' data. The monitor will visit the site to check the completeness of subject records, the accuracy of entries on the CRFs, the adherence to the protocol and to Good Clinical Practice, the progress of enrollment, and to ensure that study drug is being stored, dispensed, and accounted for according to specifications. Key study personnel must be available to assist the monitor during these visits.

The investigator must maintain source documents for each subject in the study, consisting of case and visit notes (hospital or clinic medical records) containing demographic and medical information, laboratory data, electrocardiograms, and the results of any other tests or assessments. All information on CRFs must be traceable to these source documents in the subject's file. The investigator must also keep the original informed consent form signed by the subject (a signed copy is given to the subject).

The investigator must give the monitor access to all relevant source documents to confirm their consistency with the CRF entries. Novartis monitoring standards require full verification for the presence of informed consent, adherence to the eligibility criteria, documentation of SAEs, and the recording of data that will be used for all primary and safety variables. Additional checks of the consistency of the source data with the CRFs are performed according to the study-specific monitoring plan. No information in source documents about the identity of the subjects will be disclosed.

## **10.2 Data collection**

Designated investigator staff will enter the data required by the protocol into the Electronic Case Report Forms using fully validated software that conforms to 21 CFR Part 11 requirements. Designated investigator site staff will not be given access to the EDC system until they have been trained. Automatic validation programs check for data discrepancies and, by generating appropriate error messages, allow the data to be confirmed or corrected before transfer of the data to the CRO working on behalf of Novartis. The Investigator must certify that the data entered into the Electronic Case Report Forms are complete and accurate. After database lock, the investigator will receive a CD-ROM or paper copies of the subject data for archiving at the investigational site.

Data not requiring a separate written record will be defined in the Site Operations Manual and [Assessment schedule](#) and can be recorded directly on the CRFs. All other data captured for this study will have an external originating source (either written or electronic) with the CRF not being considered as source.

## **10.3 Database management and quality control**

All data should be recorded, handled and stored in a way that allows its accurate reporting, interpretation and verification.

The CRO working on behalf of Novartis review the data entered into the eCRFs by investigational staff for completeness and accuracy and instruct the site personnel to make any required corrections or additions. Queries are sent to the investigational site using an electronic data query. Designated investigator site staff is required to respond to the query and confirm or correct the data. If the electronic query system is not used, a paper Data Query Form will be faxed to the site. Site personnel will complete and sign the faxed copy and fax it back to the CRO working on behalf of Novartis who will make the correction to the database.

Concomitant medications entered into the database will be coded using the WHO Drug Reference List, which employs the Anatomical Therapeutic Chemical classification system. Medical history/current medical conditions and adverse events will be coded using the Medical dictionary for regulatory activities (MedDRA) terminology.

Laboratory samples will be processed centrally and the results will be sent electronically to Novartis (or a designated CRO).

This will be a non-randomized study the investigator and site will be unblinded while the patient will remain blinded. The occurrence of any protocol deviations will be determined. After these actions have been completed and the database has been declared to be complete and accurate, it will be locked and the treatment codes will be unblinded and made available for data analysis. Any changes to the database after that time can only be made by joint written agreement between the COAR Analytics and TM-TA Head.

Corporate Confidential Information

## **10.4 Data Monitoring Committee**

Not required.

## **10.5 Adjudication Committee**

Not required

# **11 Data analysis**

If the 0.9 mg dose is assessed then cohort will serve as a grouping factor for all relevant data listings. Additionally the effects of cohort on different endpoints will be explored and cohort may be included as a covariate in the corresponding analysis models as needed. A separate analysis may be performed for each cohort.

## **11.1 Analysis sets**

For all analysis sets, subjects will be analyzed according to the study treatment received.

The safety analysis set will include all subjects that received any study drug.

The PK analysis set will include all subjects with available PK data and no protocol deviations with relevant impact on PK data.

The efficacy/PD analysis set will include all subjects that received any study drug and had no protocol deviations with relevant impact on efficacy/PD data.

## **11.2 Subject demographics and other baseline characteristics**

All data for background and demographic variables will be listed by Cohort and subject. Summary statistics will be provided by Cohort.

Relevant medical history, current medical conditions, results of laboratory screens and any other relevant information will be listed by Cohort and subject.

## **11.3 Treatments (study drug, rescue medication, other concomitant therapies, compliance)**

Data for study drug administration (rescue medication) and concomitant therapies will be listed by Cohort, treatment and subject as appropriate.

## **11.4 Analysis of the primary variable(s)**

### **11.4.1 Variable(s)**

Percent (%) of patients with headache response defined as very severe, severe, or moderate pain before dosing that becomes mild or nil at 30 minutes post-dosing is the primary variable.

### **11.4.2 Statistical model, hypothesis, and method of analysis**

A logistic regression analysis with baseline headache severity, CH type, dose, and dose by time interaction as fixed effects and subject as a random effect will be used to assess the effect of SOM230 on headache response over time. Dose and time will be included as categorical variables in the model. Placebo adjusted headache response rate at each time point will be provided. Headache response measurements after 100% oxygen therapy will be set to missing, which will be considered as missing at random.

The following approaches will be taken if the 0.9 mg dose is assessed in the second cohort:

Placebo adjusted headache response rate at each time point will be obtained for each of the two SOM230 doses. A linear dose-response trend test will be constructed within the logistic regression framework using a contrast with the first order orthogonal polynomial coefficients. Pairwise comparisons and further dose-response assessments will be performed as appropriate. If there is no difference between the two SOM230 doses then a comparison between the pooled SOM230 treatment and placebo will be conducted.

A subgroup analysis for non-sumatriptan users may be conducted as needed.

### **11.4.3 Handling of missing values/censoring/discontinuations**

Assuming missing at random, a subject with missing value at a time point will still contribute to the estimation of the treatment effect at that particular time point as the likelihood-based repeated measures analysis borrows information from non-missing values of this subject and other subjects.

#### **11.4.4 Supportive analyses**

Additionally 100% oxygen therapy will be included in the logistic regression model described above as a time dependent covariate so headache response measurements after 100% oxygen therapy can be included in the analysis.

The McNemar test with or without stratification by CH type may also be used to compare headache response rates between treatments at each time point.

A Cox proportional hazard model with dose and CH type as classification factors and headache severity as a time dependent covariate will be used to analyze time to 100% oxygen therapy. A random subject effect will be included in the model as well to account for the correlation among measurements from the same subject. Percentage of subjects receiving 100% oxygen therapy at each time point will be tabulated by treatment.

Joint modelling of the headache response and time to 100% oxygen therapy data may be attempted as appropriate.

Finally to avoid reducing statistical efficiency due to analyzing the dichotomized data the headache severity measurements over time may be analyzed using a proportional-odds model similar to the aforementioned logistic regression model.

### **11.5 Analysis of secondary and exploratory variables**

#### **11.5.1 Efficacy / Pharmacodynamics**

Pain free data will be analyzed using the same approach described for the primary variable.

A generalized linear model with CH type and dose as fixed effects and subject as a random effect will be used to compare the number of headache attacks following SOM230 treatment to baseline assuming the underlying data distribution is Poisson. Over dispersion, if any, will be accounted for as appropriate.

Corporate Confidential Information

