## **6.9      Rescue medication**

Subjects will be allowed to use 100% oxygen as rescue medication during the study as described in [Section 7.1](#). If subjects require use of other rescue medication, they must contact the site immediately to be discontinued from the study. Every effort must be made to obtain study data for at least 24 hours after study medication has been administered. Use of rescue medication must be recorded on the Concomitant medications/Significant non-drug therapies CRF after start of study drug.

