## 8 Procedures and assessments

**Table 8-1 Assessment Schedule, (Cohorts 1 &2)**

 Visit structure given for internal programming purpose only.

 In the event the subject requires SOC treatment for CH or a recurrent CH attack, the subject must contact the site, every effort must be made to discontinue the subject after 24 hours of taking the study medication, all EOS evaluations should be performed if a subject is discontinued.

 If subject is not domiciled in a clinic for the study, study drug will be administered at home, before study visits.

 If possible in Period 1, the subject may have a follow-up visit as soon as possible within 24 hours of the dose. The collected PK sample must be obtained as soon as the patient arrives to the clinic. The date, time and the time the subject took the study medication must be collected on the eCRF. If logistically not possible the sample may be collected by a visiting nurse or equivalent.

4-a In Period 2, the subject must have a follow up visit as soon as possible within 24 hours of the dose for ECG & to collect PK samples. The sample must be collected as soon as the patient arrives to the clinic. If logistically not possible the sample may be collected by a visiting nurse or equivalent. The date, time and the time the subject took the study medication must be collected on the eCRF. In case the follow-up visit in Period 2 falls on a weekend, a window of up to 48 hours may be considered.

 A second PK sample will be collected 1-2 hours after the 1st sample was collected; the collection time of PK samples must be entered in eCRF. The second PK can be optional if not logistically possible.

 If subject is not domiciled in a clinic for the study, the study drug and instructions for use will be dispensed to the subject to be used as out-patient.

 Subjects will take 2 injections (in Cohort 1) / 1 injection (in cohort 2) of SOM230 or placebo s.c. in each study Period (1 &2) as instructed. These injections must be administered at the same time one after the other. The date and time of dose must be recorded on the patient diary.

 Diary: issued at screening visit; baseline information should be collected only for last 3 days prior to the baseline visit. Diary will be reviewed at the clinic visits.

 Blood chemistry should be repeated if Baseline Visit is greater than 10 days from Screening Visit.

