 The EOS visit will occur 3 days after Period 2, post study drug administration.

 At the Investigator's discretion, optional screening ECG may be performed. The baseline ECG is optional, if screening ECG is done within not more than 7 days, and there is no change in medications. All subjects must have one ECG performed, either at screening or baseline, prior to the treatment phase.

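### The exploratory Poisson model for attack counts has no visible term for observation time, so follow-up cut short after SOM230 would read as fewer attacks

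*Protocol*

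**What the plan says.** **Model.** Protocol 11.5.1 specifies a mixed model whose purpose is to "compare the number of headache attacks following SOM230 treatment to baseline assuming the underlying data distribution is Poisson". Its terms are two fixed effects, for CH type and for dose, and a random effect for subject. The one further provision is "Over dispersion, if any, will be accounted for as appropriate". No offset, person-time or per-day response is named. The visible SAP text does not carry this model.

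**Windows.** For baseline, Table 8-1 footnote 8 says "baseline information should be collected only for last 3 days prior to the baseline visit". For follow-up, footnote 10 says "The EOS visit will occur 3 days after Period 2, post study drug administration". A subject who completes therefore has 3 days on each side.

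**Early stopping.** Protocol 6.9 says that subjects who need rescue medication other than oxygen "they must contact the site immediately to be discontinued from the study", and adds "Every effort must be made to obtain study data for at least 24 hours after study medication has been administered". Table 8-1 footnote 2 says of subjects who need standard-of-care treatment that "every effort must be made to discontinue the subject after 24 hours of taking the study medication". Protocol 7.1 keeps the data collected until then.

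**Scale of interest.** Protocol 11.7 powers attack frequency on a difference of 0.5 attacks per day. Protocol 3.2 also speaks of attacks per day.

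**The concern.** Raw Poisson counts can be compared only when observation time is equal or is modelled. Here a subject discontinued after SOM230 can contribute about 1 day of counts against 3 baseline days. The random subject effect does not absorb this, because the inequality lies within the subject, between the two windows.

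No visible rule removes these subjects or corrects for the short window. SAP Table 4-1 excludes prohibited treatment only in the 24 hours before dosing and the first 30 minutes after it. The missing-data text (Protocol 11.4.3, SAP 6.1.3.2) concerns response at time points, not shortened count windows.

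Shorter observation can only lower the post-dose count, so the artefact always points towards fewer attacks after SOM230. At stake is the exploratory statement that a dose reduces later attacks.

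**Working it through.** **Inputs from the documents.** 23 subjects, one-sided 0.05, SD 0.84, correlation 0.5, difference 0.5 attacks/day (Protocol 11.7); 2 to 6 attacks/day at entry (4.1); 3-day windows and the 24-hour minimum (Table 8-1, 6.9).

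**Assumed.** f, the share observed for 1 day instead of 3 after SOM230, is taken as 5%, 10% and 20%. In 23 subjects that is 1.2, 2.3 and 4.6 people. Stopping is taken as independent of attack rate.

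**The plan's own figure.** SD of the paired difference = 0.84 × sqrt(2 × (1 - 0.5)) = 0.84. Noncentrality = 0.5/0.84 × sqrt(23) = 2.85 on 22 df. One-sided power is 86.9%, which agrees with the stated 86%. That calculation is on a per-day scale.

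**Expected ratio with no drug effect.** At a true rate of m attacks/day, the expected baseline count is 3m. The expected post-dose count is (1 - f) × 3m + f × m = 3m - 2fm. The ratio is 1 - 2f/3, and the apparent fall is m × 2f/3 attacks/day.

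| f | ratio | apparent fall at 2/day | at 4/day | at 6/day |
|---|---|---|---|---|
| 5% | 0.97 | 0.07 | 0.13 | 0.20 |
| 10% | 0.93 | 0.13 | 0.27 | 0.40 |
| 20% | 0.87 | 0.27 | 0.53 | 0.80 |

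The planned difference is 0.5 attacks/day.

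**False-positive rate.** 20,000 null trials of 23 subjects were simulated per setting, with Poisson counts at 2, 4 and 6 attacks/day. The log count ratio was tested one-sided at 5%, first plain, then with the standard error scaled by the Pearson overdispersion estimate (not allowed below 1), and then with days observed as an offset. The 5% level is borrowed from 11.7, because 11.5.1 sets none.

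| f | no offset, unscaled | no offset, scaled | offset |
|---|---|---|---|
| 5% | 9-15% | 7-10% | about 5% |
| 10% | 16-28% | 12-18% | about 5% |
| 20% | 33-60% | 25-39% | about 5% |

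Ranges run from 2 to 6 attacks/day. The scaled column is the fairer reading of the plan, since 11.5.1 provides for overdispersion and mixing 1-day and 3-day windows produces it. Scaling widens the standard error but leaves the ratio biased.

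**The case against.** **The variable may already be a daily rate.** The exploratory objectives are redacted in both documents, and redacted text follows the model paragraph. Where attack frequency is visible elsewhere, it is per day. A reader might infer that the plan ignores exposure; the documents do not establish that. They establish only that the visible model sentence is grammatically complete and names a count with no exposure term.

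**A reader might take f as 20% from the drop-out allowance.** Protocol 11.6 does not support this. The 23 subjects are already net of drop-out (23/0.8 = 28.75, hence about 30 enrolled). The allowance can also cover losses before SOM230, such as no attack within 72 hours or other rescue in Period 1, and those subjects have no post-SOM230 count. So 20% is only an illustrative upper value here.

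**A reader might quote the unscaled 33-60%.** That leaves out the plan's own overdispersion provision.

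**A reader might take 24 hours as all the data that will exist.** Protocol 6.9 states it as a minimum, and footnote 2 also asks for the end-of-study evaluations at discontinuation. Some stopped subjects may be observed for longer, which shrinks the bias.

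**An offset is not a full remedy.** Subjects stop because they need further treatment, so their observed day may not represent the days not seen. This objection stands.

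**The analysis is exploratory in a non-confirmatory study.** This also stands and limits the weight of the point. It does not justify leaving observation time out of a count model when one term supplies it.

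**Conclusion.** The point holds on the visible text, in a limited form. If everyone is followed for 3 days there is no bias. If a share f is seen for only 1 day, the null ratio is 1 - 2f/3, always in favour of SOM230. The scaled false-positive rate rises from the nominal 5% to about 7-10% at f = 5%, 12-18% at 10% and 25-39% at 20%.

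These figures rest on an assumed f, a 1-day window for stopped subjects, stopping unrelated to attack rate, and a test level borrowed from 11.7. They also assume that redacted text does not already define attacks per observed day.

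A reader might extend the bias to the main efficacy conclusion. The documents do not support that: headache response and pain-free response are assessed 30 minutes after dosing and do not depend on the length of follow-up.

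**What to change.** - In Protocol 11.5.1, add log(days of diary observation) as an offset, separately for the baseline and post-SOM230 windows, so that the model compares attacks per observed day as 11.7 does. Make the same change in the SAP if the model is carried there. If redacted text already defines a daily rate, align the model sentence with it.
- State as a limitation that the offset corrects unequal observation time but not discontinuation related to outcome. Report the number of subjects with shortened follow-up and their days observed.
- Reconcile the passages on permitted rescue: Protocol 3.1 and 6.9 allow only 100% oxygen, while SAP 1.4 also lists sumatriptan. The answer determines who stops early, and so f.

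The cost is one model term and a few sentences. Dose times and diary entries are already collected.

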#### **11.5.2 Safety**

##### **Vital signs**

All vital signs data will be listed by treatment, subject, and visit/time and if ranges are available abnormalities (and relevant orthostatic changes) will be flagged. Summary statistics will be provided by treatment and visit/time.

